14.7.2. Handling of Missing Data

Element	Reporting Detail
General	
 • Missing data occurs when any requested data is not provided, leading to blank fields on the collection instrument: 
 ○ These data will be indicated using a “blank” in data listings. Where all data for a specific visit are missing the visit will be excluded from the listing. ○ Answers such as “Not applicable” and “Not evaluable” are not considered to be missing data and should be displayed. 
Values reported as ‘BLQ’ are not considered as missing data and are handled as detailed in

Element	Reporting Detail
	Section 14.6.6, these values will be displayed in the listings and included in any summary/analysis outputs.
Outliers	
 All data will be included in the summaries and analyses of each endpoint. The exclusion of participants or participant data from any supplementary analyses will be documented within footnotes and where required the clinical study report.
Covariate information	
 Participants with missing information for a covariate included in the analysis model will be excluded from the analysis.

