7.2.4.4. Statistical Analyses / Methods

Endpoint / Variables					

 The proportion of subjects requiring at least one course of systemic steroids for nasal polyps up to Week 52 					
Model Specification					

 A logistic regression model will be used to compare the proportion of participants requiring a course of systemic steroids up to week 52 in the mepolizumab arm compared to placebo. The odds ratio comparing treatment groups will be estimated using the observed marginal distribution of the sample covariates. The analysis model will include the following terms: 
 
 Fixed Categorical:	Treatment group, Region	
 
 Fixed Continuous:	Number of OCS courses for NP in last 12 months (0, 1, >1; ordinal), baseline total endoscopic NP score (based on centrally read data), baseline nasal obstruction VAS score, Log_e baseline blood eosinophil	
 
 		Fixed Categorical:	Treatment group, Region	Fixed Continuous:	Number of OCS courses for NP in last 12 months (0, 1, >1; ordinal), baseline total endoscopic NP score (based on centrally read data), baseline nasal obstruction VAS score, Log _e baseline blood eosinophil
Fixed Categorical:	Treatment group, Region				
Fixed Continuous:	Number of OCS courses for NP in last 12 months (0, 1, >1; ordinal), baseline total endoscopic NP score (based on centrally read data), baseline nasal obstruction VAS score, Log _e baseline blood eosinophil				

 Participants with missing covariate information will be excluded from the analysis 					
Model Checking & Diagnostics					

 Models will be checked for issues with convergence 					
Model Results Presentation					

 The number and percentage of participants identified as requiring at least one course of systemic steroids for nasal polyps will be displayed by treatment group, as will the number of courses of therapy required. The estimated odds ratio, 95% CI and p-value comparing treatments from the logistic regression model will be displayed. 					
Subgroup Analyses					

 No subgroup analyses are planned for this endpoint. 					
Sensitivity and Supportive Analyses					

 No sensitivity/supportive analyses are planned for this endpoint. 					

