7.3. Other Efficacy Analyses

7.3.1. Total Endoscopic Nasal Polyps Score Responders

A responder is defined as a participant achieving a ≥ 1 -point improvement (decrease) from baseline in total endoscopic NP score (based on centrally read data) at Week 52. Participants with missing data at Baseline or Week 52 (due to early study withdrawal or any other reason) will be included in the analysis as a non-responder.

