7.3.1.4. Statistical Analyses / Methods

Endpoint / Variables					

 Total endoscopic nasal polyps score responders Participants with a ≥ 1-point improvement from baseline in total endoscopic NP at Week 52 (based on centrally read data) will be included in the analysis as a responder. The following participants will be included in the analysis as a non-responder: 
 Participants who had actual surgery prior to Week 52 Participants who withdrew early from the study or who had missing data at Baseline or Week 52 					
Model Specification					

 A logistic regression model will be used to compare the proportion of responders in the mepolizumab arm compared to placebo. The odds ratio comparing treatment groups will be estimated using the observed marginal distribution of the sample covariates. The analysis model will include the following terms: 
 
 Fixed Categorical:	Treatment group, Region	
 
 Fixed Continuous:	Baseline score, Log_e baseline blood eosinophil count	
 
 
 Participants with missing covariate information will be excluded from the analysis 		Fixed Categorical:	Treatment group, Region	Fixed Continuous:	Baseline score, Log_e baseline blood eosinophil count
Fixed Categorical:	Treatment group, Region				
Fixed Continuous:	Baseline score, Log_e baseline blood eosinophil count				
Model Checking & Diagnostics					

 Models will be checked for issues with convergence. 					
Model Results Presentation					

 The number and percentage of participants identified as responders and non-responders for analysis will be displayed by treatment group, the non-responder group will be further categorized to display the number of participants with actual surgery, the number withdrawn early from the study and the number with missing baseline data. The estimated odds ratio, 95% CI and p-value comparing treatments from the logistic regression model will be displayed. A forest plot of the estimated odds ratio and 95% CI for the comparison of treatment groups will be provided by visit. 					

Subgroup Analyses

- No subgroup analyses are planned for this endpoint.

Sensitivity and Supportive Analyses

- No sensitivity/supportive analyses are planned for this endpoint.

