7.3.3.4. Statistical Analyses / Methods

Endpoint / Variables

 • Participants with a ≥ 8.9-point improvement from baseline in SNOT-22 score at Week 52 will be included in the analysis as a responder. • The following participants will be included in the analysis as a non-responder: 
 ○ Participants who had actual surgery prior to Week 52 ○ Participants who withdrew early from the study or who had missing data at Baseline or Week 52
Model Specification

 • See Section 7.3.1.4
Model Checking & Diagnostics

 • See Section 7.3.1.4
Model Results Presentation

 • See Section 7.3.1.4

Subgroup Analyses

- No subgroup analyses are planned for this endpoint.

Sensitivity and Supportive Analyses

- No sensitivity/supportive analyses are planned for this endpoint.

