14.6.5. Efficacy

Assigning the worst score for subjects with surgery or missing data
Relevant efficacy endpoints

 Subjects who undergo surgery/sinuplasty will have their worst observed score (or worst observed 4-week mean) assigned for all subsequent visits (or 4-week periods) following surgery/sinuplasty. The assigned value will be the worst observed value from baseline up to before the surgery/sinuplasty. Assessments taking place on the same day as surgery/sinuplasty are assumed to have been carried out before the surgery/sinuplasty. Subjects who have not experienced surgery/sinuplasty and have missing values due to study withdrawal, will have their worst observed score (or worst observed 4-week mean) assigned for all missing visits (or 4-week periods) following study withdrawal. The assigned value will be the worst observed value from baseline up until study withdrawal. Subjects with missing data for other reasons will have their worst observed score (or worst observed 4-week mean) prior to the missing visit (or missing 4-week period) assigned.
Total Endoscopic Nasal Score
Responder

 A responder will be defined as a participant with a ≥1-point improvement from baseline in total endoscopic nasal score (centrally read). Participants with no improvement/worsening or with missing data will be considered a non-responder for analysis.
VAS scores (individual and composite)
Individual VAS Scores

 VAS scores are captured electronically using an eDiary. participants indicate their response on a line CCI - This section contained Clinical Outcome Assessment data collection questionnaires or indices, which are protected by third party copyright laws and therefore have been excluded. The final VAS scores for inclusion in summary and analysis tables will be derived from the electronically captured score by CCI.
Change from baseline categories

 The baseline scores will be calculated as the mean of the scores reported between the 7 days prior to the first dose. The scores for each 4-week period will be calculated as the mean of the scores reported between timepoints detailed in Section 14.3.3.
Composite VAS scores

VAS scores (individual and composite)

- Two separate composite VAS scores will be derived using the final VAS scores:
- Composite of nasal obstruction, nasal discharge, mucus in the throat and loss of smell

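### SAP 7.3.1.4, 7.3.3.4 and 7.3.5.4 count participants with a missing baseline as failures, but the covariate rule removes them from the odds ratio for the same endpoint

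*SAP*

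**What the plan says.** All references are to the current SAP (RAP Amendment 1).

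- **Inclusion rule.** Section 7.3.1 says of nasal polyp (NP) score responders: "Participants with missing data at Baseline or Week 52 (due to early study withdrawal or any other reason) will be included in the analysis", as non-responders. The methods box in 7.3.1.4 repeats this, listing among the non-responders: "Participants who withdrew early from the study or who had missing data at Baseline or Week 52". Section 7.3.3.4 (SNOT-22 responders) has the same list. Section 7.3.5.4 has it for participants still counted as needing surgery. Section 14.6.5 is consistent but does not name Baseline: "Participants with no improvement/worsening or with missing data will be considered a non-responder for analysis".
- **Display.** The 7.3.1.4 results must break the non-responder group down to show, among others, "the number withdrawn early from the study and the number with missing baseline data". Section 7.3.5.4 asks for the equivalent breakdown.
- **Model.** The logistic model in 7.3.1.4 has "Baseline score" as a continuous term. The SNOT-22 box takes its model by reference: "See Section 7.3.1.4". The need-for-surgery model contains baseline NP score and baseline overall VAS.
- **Exclusion rule.** Section 14.7.2 sets the general rule: "Participants with missing information for a covariate included in the analysis model will be excluded from the analysis". The boxes in 7.3.1.4 and 7.3.5.4 carry it too, in the wording also used in 7.2.4.4: "Participants with missing covariate information will be excluded from the analysis".

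**The concern.** A participant with no baseline score is told to be in the analysis as a failure and, in the same box, told to be out of it. Standard software settles the matter by dropping the record when the covariate is blank. The percentages and the odds ratio for one endpoint would then rest on different participants, and the failure rule would never reach the estimate, its interval or its p-value. If the SAP does not say which rule governs, the choice falls to whoever programs the model, possibly after unblinding.

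**Working it through.** The plan gives no figure to reproduce here. The check sets the rules side by side and then illustrates the size.

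**Rules applied to one participant with a missing baseline score**

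| Output | Rule that acts | Result |
|---|---|---|
| n (%) in 7.3.1.4, 7.3.3.4, 7.3.5.4 | Inclusion | Counted as a failure |
| Odds ratio, CI, p-value | Exclusion (box and 14.7.2) | Not in the model |

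A logistic fit to 400 simulated participants confirmed this. Twelve had the baseline covariate blank and were coded as failures, and the fit used 388 records.

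**Who can have a missing baseline**

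- NP score: if Day 1 is missing, SAP 5.2.1 uses the preceding central read. Randomisation criterion 1 (Protocol 6.3) requires a centrally read Visit 1 score.
- Overall VAS: randomisation criteria 2 and 5 require a 7-day mean above 7 and diary entries on 4 of the last 7 days before Visit 2.
- SNOT-22: first scheduled at Visit 2 (Protocol Section 2), with no entry criterion behind it. This is the exposed endpoint.

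**Size**

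Inputs: 200 per arm and, purely as illustrative rates among those with a baseline, 27% on placebo (p0) and 52% on mepolizumab (p1). All come from Protocol 10.1, where the rates are for a one-point NP improvement in the earlier Phase II study. The numbers missing, m0 (placebo) and m1 (mepolizumab), are assumptions. Odds ratios are unadjusted.

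- Exclusion: OR = [p1/(1 − p1)] / [p0/(1 − p0)] = (0.52/0.48)/(0.27/0.73) = 2.93, whatever m0 and m1 are.
- Failure rule: each rate becomes p × (200 − m)/200. With 5 missing per arm, 0.52 × 195/200 = 0.507 and 0.27 × 195/200 = 0.263, so OR = (0.507/0.493)/(0.263/0.737) = 2.88.

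| m0 (placebo) | m1 (mepolizumab) | OR, exclusion | OR, failure rule |
|---|---|---|---|
| 0 | 0 | 2.93 | 2.93 |
| 2 | 2 | 2.93 | 2.91 |
| 5 | 5 | 2.93 | 2.88 |
| 10 | 10 | 2.93 | 2.83 |
| 0 | 5 | 2.93 | 2.78 |
| 5 | 0 | 2.93 | 3.03 |
| 0 | 10 | 2.93 | 2.64 |
| 10 | 0 | 2.93 | 3.14 |

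**The case against.** The strongest reply is that the affected set is nearly empty. For NP score and overall VAS, a missing baseline needs an entry violation or lost data. SNOT-22 is completed electronically under supervision (Protocol 9.2.7.1) and before other assessments, and up to half the items may be missing and imputed (SAP 14.6.5). All three endpoints are classed as other and are absent from the hierarchy in SAP 5.5. This stands, and it limits the size of the point.

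A second reply is that the inclusion rule was meant only for the counts, with the odds ratio a complete-case estimate. That reading is workable, but the SAP does not state it and describes both rules as governing the analysis. For need for surgery, the text in 7.3.5 and 14.6.5 mentions only missing Week 52 data. The Baseline clause is in 7.3.5.4 alone, but it is explicit there.

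Three stronger readings are tempting, and the documents do not support them.

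- *The confirmatory models contradict themselves or abandon ITT.* The time-to-surgery Cox model (7.2.1.4) and the systemic-steroid model (7.2.4.4) also exclude participants with missing covariates, including number of previous surgeries and number of OCS courses. Neither section has a competing inclusion rule. This is a disclosed complete-case rule on pre-treatment items, and its expected cost is precision rather than between-arm bias. Surgical history and OCS use are collected at screening, and nothing suggests that gaps are expected.
- *Every model box repeats the exclusion.* The UPSIT box (7.3.9.1) does not, and 7.3.3.4 has it only by reference. Section 14.7.2 is nevertheless general.
- *The odds ratio could move a lot.* The larger shifts in the table need one-sided missingness in a pre-treatment measure, which randomisation would produce only by chance.

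**Conclusion.** The contradiction is real. It sits inside 7.3.1.4 and 7.3.5.4 and reaches 7.3.3.4 by reference, and nothing elsewhere in the SAP resolves it. As written, the missing-baseline failure rule affects the percentages but not the inference.

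The consequence is probably small: 2.88 against 2.93 with an assumed 5 missing per arm, and nothing if no baseline is missing. The documents give no expected number of missing baselines and no SNOT-22 responder rate, so these figures show scale and are not a forecast. No hierarchy endpoint is affected by the contradiction. It should be settled before unblinding because a correction is cheap and leaves no choice to the programmer.

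**What to change.** In 7.3.1.4 and 7.3.5.4, and therefore in 7.3.3.4, replace the exclusion line with: *A missing baseline covariate is replaced by the pooled (both arms) ITT mean, so that the participant stays in the model as a non-responder or as still needing surgery.* Add to 14.7.2 that its rule applies unless Section 7 states otherwise, so that the general rule does not reinstate the conflict. The imputation ignores treatment arm and uses pre-treatment values, so it does not favour either group.

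As an optional improvement, not the correction of an error, the same imputation could be used in 7.2.1.4 and 7.2.4.4, with the most frequent category for the ordinal history items. ITT participants with a known outcome would then be kept.

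It should not be extended to the PK model in 10.3.3, which uses the PK population. Nor does it help change-from-baseline endpoints whose own baseline is missing, because 14.6.4 then sets the outcome itself to missing.

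Cost: a sentence in each of two boxes, a clause in 14.7.2 and a few lines of code. The downside is slightly diluted covariate adjustment for the few imputed values.

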14.7.2.1. Handling of Missing Dates

Element	Reporting Detail
General	
Start or end dates which are completely missing (i.e. no day, month or year is specified) will remain missing, with no imputation applied.
 
Derivations requiring this information such as time to onset and duration will be set to missing.

14.7.2.2. Handling of Partial Dates

Element	Reporting Detail
General	
 Partial dates will be displayed as captured in subject listings.
Adverse Events	
 The eCRF allows for the possibility of partial dates to be recorded for AE start and end dates. For partial dates the following imputations will be applied: 
 Partial Start Date: '01' will be used for a missing day and 'Jan' will be used for a missing month. If this results in a date prior to the start of study treatment, then the treatment start date will be used. The event will then be considered 'On-treatment' as per Section 14.4.1.3. Partial Stop Date: '28/29/30/31' will be used for a missing day (dependent on the month and year) and 'Dec' will be used for a missing month. If this results in a date after the study stop date, then the study stop date will be used. The above imputations will be applied when calculating the time to onset and duration of the event.
Concomitant Medications	
 For concomitant medications partial dates will be imputed as follows: 
 Partial start date: '01' will be used for a missing day and 'Jan' will be used for a missing month Partial stop date: '28/29/30/31' will be used for a missing day (dependent on the month and year) and 'Dec' will be used for a missing month.

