14.4.1.4. Phases for Concomitant Medication Start Dates

Study Phase	Definition
Pre-Treatment (Started prior to treatment)	Concomitant medication (CM) start date < IP start date
On-Treatment (Started during Treatment)	If CM start date is on/after IP start date & on/before IP stop date +28 days. (IP Start Date ≤ CM Start Date ≤ IP Stop Date + 28 days)
Post-Treatment (Started post- treatment)	If CM start date is after the IP stop date + 28 days. (CM Start Date > IP Stop Date + 28 days)
Follow-Up After Week 52 (started during the Follow- up period after Week 52)	Participants who enter the follow-up period after Week 52: If CM start date is after the Week 52 Visit date.

NOTES: If the IP stop date is missing and/or the CM start date is missing then the CM is considered to have started on-treatment

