
 The total number of mgs of prednisolone equivalent OCS use per year will be calculated as follows and will be based on systemic steroids taken via the following routes: Oral, Intravenous, Intramuscular: $\left(\frac{\text{Total cumulative mgs prednisolone – equivalent OCS use in period}}{\text{Total number of days in period}} \right) * 365.25$ 
 The following table from the study reference manual will be used for conversion of intravenous and oral steroid use into prednisolone equivalent OCS use in mgs:

Systemic steroid use	
Glucocorticoid	Approximate equivalent dose (mg)
Short-Acting	
Cortisone	25
Hydrocortisone	20
Intermediate-Acting	
Methylprednisolone	4
Prednisolone	5
Prednisone	5
Triamcinolone	4
Long- Acting	
Betamethasone	0.6-0.75
Dexamethasone	0.75

- Participants who withdraw early from the study will have yearly use estimated based on use during the study.

Courses of Therapy

- A course of systemic steroid therapy is defined by the start and stop date of therapy.
- If the start date of a course of systemic steroid therapy occurs <7 days from the stop date of the previous course, it will be considered a continuation of the same course.

Days on Therapy

- The duration of a course of systemic steroids will be calculated as the number of days between the start and stop date of the course: stop date – start date + 1
- For each participant the total number of days on systemic steroids will be calculated as the sum of the duration of each of their courses of therapy.
- For each participant the percentage of days on systemic steroids will be calculated as follows:

$$\left(\frac{\text{Total number of days on systemic steroids}}{\text{Total number of days in the study}} \right) * 100$$

Nasal Surgery or Course of Systemic Steroids

Time to first nasal surgery or course of systemic steroids

- Calculated as (Date of first nasal surgery/course of systemic steroids – Date of first dose of study treatment) + 1
- Analysis excluding data reported in the follow-up period after Week 52:
For participants who withdraw from the study before Week 52 and before experiencing either event, event times will be censored at the time of study withdrawal
For participants who complete to Week 52 without experiencing either event, event times will be censored at the time of the Week 52 visit

Antibiotic Use
Courses of Therapy

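### SAP 14.7.2.2 gives partial steroid dates no treatment-start floor or study-stop cap, so some courses can be dated before first dose or past study end

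*SAP*

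**What the plan says.** **Partial dates (SAP 14.7.2.2).** The adverse-event and concomitant-medication rows fill dates identically. Start: "Partial Start Date: '01' will be used for a missing day and 'Jan' will be used for a missing month". Stop: "Partial Stop Date: '28/29/30/31' will be used for a missing day (dependent on the month and year) and 'Dec' will be used" when the month is missing. The adverse-event row adds two limits: "If this results in a date prior to the start of study treatment, then the treatment start date will be used", and "If this results in a date after the study stop date, then the study stop date will be used". The concomitant-medication row has neither.

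**Steroids fall under that row.** Listing 13 (SAP 14.12.15) holds the systemic-corticosteroid eCRF entries within concomitant medications, and no separate partial-date rule is given for them. Courses are built from dates (SAP 14.6.5): "A course of systemic steroid therapy is defined by the start and stop date of therapy".

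**The endpoint.** SAP 7.2.4.4 analyses "The proportion of subjects requiring at least one course of systemic steroids for nasal polyps up to Week 52". It is fourth among the secondary endpoints in SAP 5.5. The number of days on steroids, mg per year, time to first course, and time to first surgery or course are other endpoints (SAP 7.3.12 and 7.3.14).

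**Phases.** Under SAP 14.4.1.4 a medication started pre-treatment if "Concomitant medication (CM) start date < IP start date". Under SAP 14.4.1.5 one that starts before first dose and stops on or after it was taken during treatment. For a wholly missing start, 14.4.1.4 says: "If the IP stop date is missing and/or the CM start date is missing then the CM is considered to have started on-treatment". Section 7.2.4 does not say which phase definition selects courses.

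**The concern.** The two rows make the same fill, but only one is protected from its side effects. Without a floor, a course given on study can be dated before first dose. Without a cap, a short course can run past the end of the participant's follow-up. A start known to the right month can also be treated less favourably than a start not known at all, which counts as on-treatment.

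Three things are at stake. A steroid user could become a non-user in a multiplicity-controlled endpoint for which no sensitivity analysis is planned. The surgery-or-steroid Cox model and the time-to-first-course curve could receive unusable times. Days on steroids could be overstated, and a stretched course could absorb a later one through the rule that joins courses less than 7 days apart.

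**Working it through.** The documents state no rate or power for the steroid endpoint, so there is no planned figure to reproduce. The check applies the written rule.

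**1. Example.** Illustrative first dose: 15 March 2018. Event day = start − first dose + 1 (SAP 14.6.5, surgery or course).

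| Recorded start | Imputed start | Event day | Start-date phase | Usage phase |
|---|---|---|---|---|
| March 2018 | 1 Mar 2018 | −14 + 1 = −13 | pre-treatment | during |
| 2018 | 1 Jan 2018 | −73 + 1 = −72 | pre-treatment | during |
| June 2018 | 1 Jun 2018 | 78 + 1 = 79 | on-treatment | during |
| 2019 | 1 Jan 2019 | 292 + 1 = 293 | on-treatment | during |

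Only the month or year of first dose is affected. The usage column holds because the stop, true or imputed, is on or after first dose.

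**2. Is the pre-dose date wrong?** Protocol 6.2 (exclusion 18) bars systemic steroids for 4 weeks before screening, and 6.3 (criterion 9) bars a course in the nominal 4-week run-in: 28 + 28 = 56 days.
- *Month-only, first-dose month.* The 1st is at most 30 days before first dose, inside the 56. For an eligible participant the course must be on study, so the imputed phase is wrong.
- *Year-only, first-dose year.* With first dose on day d of the year, permitted pre-study days are d − 56 and remaining on-study days are 365 − d. They are equal at d = 210.5 (late July). For 1 October (d = 274) they are 218 and 91. A year-only date can therefore be genuine history.

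**3. Share of on-study courses moved before first dose.** Simulation of 200,000 courses for each of three true lengths (5, 10 and 14 days); assumptions: first dose uniform over a calendar year, onset uniform over the next 364 days.
- Year-only start: about 50%.
- Month-only start: about 4% (about half a month remains on average, 15/364 = 4.1%).

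**4. Loss from the endpoint, under start-date phasing only.** Loss = steroid use × share of users whose single course is partially dated × share moved. The first two are assumptions (30–50% and 0.5–5%).
- Year-only: 0.30 × 0.005 × 0.50 = 0.08 points, up to 0.50 × 0.05 × 0.50 = 1.25 points.
- Month-only: 0.30 × 0.005 × 0.04 = 0.006 points, up to 0.50 × 0.05 × 0.04 = 0.10 points.

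**5. Duration (stop − start + 1) of a true 5–14 day course, same simulation.**
- Both dates year-only: mean 369–378 days (365 within one year, 730–731 across two).
- Both month-only: mean 34–43 days, maximum 62.
- Only the stop year-only: mean 187–196 days.
- The imputed stop passes Week 52 in 51–53% (year-only) or 5–7% (month-only).

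A participant who leaves on day 100 with one year-only course scores 365/100 = 365% of study days on steroids. One 7-day course stretched to 365 days adds (365 − 7)/200 = 1.79 days to the mean of a 200-participant arm.

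**6. Does the adverse-event floor suffice?** In the example it moves the year-only start to 15 March, but the course still runs to 31 December: 365 − 73 = 292 days unless an earlier cap applies. A bound on duration is needed too.

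**The case against.** **Partial dates should be rare.** Protocol 7.6 requires start and end dates, 9.2.4 records OCS dose and duration in the eCRF, and the schedule of activities has OCS assessed at every visit from Visit 2. This stands, and it is why the likely effect is small. But the SAP provides for partial dates, and a rule should give sound results when used.

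**The adverse-event limits do not transfer directly.** Adverse events are collected only from start of treatment (Protocol 9.3.1), so a floor cannot misplace them. Medications are recorded from pre-screening (9.1.1) and OCS history is taken at screening. This stands for year-only starts, as step 2 shows: a blanket floor could turn history into Day 1 use. It does not stand for a month-only steroid start in the first-dose month.

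**Nothing says courses are selected by start-date phase.** This also stands. A reader might infer that real courses do drop out of the fourth secondary endpoint. The SAP supports that only under 14.4.1.4; under 14.4.1.5 the course is kept. Its event time is still non-positive either way.

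**The summaries are limited to Week 52** (SAP 7 and 7.3.12). That limits which reported data enter. It does not say that an imputed stop is truncated.

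**Conclusion.** The rule should be changed. For a month-only steroid start in the month of first dose it gives a wrong phase and a non-positive event time in any eligible participant, unless first dose was on the 1st. For a year-only start in the first-dose year it may do so. Without a cap, days on steroids can exceed days in study.

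The effect on the confirmatory endpoint is probably small: about 0.006–0.10 points (month-only) or 0.08–1.25 points (year-only). These figures rest on the assumed use and partial-date rates, uniform timing, one course per affected user, and start-date phasing. The true frequency of partial dates is unknown, and nothing shows a difference between arms.

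Stronger readings are not supported:
- Month-only stops go to month end, not 31 December, unless the month is December.
- Year-only starts in the second calendar year stay on study.
- mg per year is inflated only if cumulative mg is built from imputed duration, which the SAP does not state.
- Days and mg are other endpoints, summarised only.
- The treatment of wholly missing starts is an asymmetry, not a contradiction: the SAP handles the two cases separately.

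**What to change.** In SAP 14.7.2.2, before unblinding, for systemic-steroid and antibiotic records:

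1. If the known month and year equal those of first dose and the imputed start falls earlier, set the start to the first-dose date. Antibiotics are not barred before dosing, so for them add the visit condition in item 2.
2. For year-only starts, apply that floor only to records reported at a post-baseline visit, not to screening history.
3. Cap the imputed stop at the earliest of the Week 52 visit (end of follow-up for the follow-up summaries), withdrawal or study stop. Where the eCRF holds a duration, use it to bound the course.
4. State in 7.2.4 and 14.6.5 that the steroid endpoints count courses starting on or after first dose and up to Week 52. This settles the choice of phase. It also covers courses floored to the first-dose date, which the strict inequalities in 14.4.1.5 would leave unclassified, and it excludes pre-study courses stretched past first dose by a partial stop.

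The cost is a few sentences, a little extra programming, and a small chance that a pre-study year-only course is counted as on study.
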